## Overview and hypothesis

More than one million patients present to US emergency departments (ED) annually to obtain relief from an acute migraine. Nearly twenty different medications are commonly used to treat acute migraine in the ED, yet the goal of sustained headache relief remains elusive. Fewer than 25% of ED migraine patients achieve freedom from their headache and remain headache free for 48 hours, regardless of which medication they receive. Medications commonly used to treat acute migraine are burdened by a host of nuisance side effects including drowsiness, dizziness, and restlessness. There remains a need for an acute migraine intervention that can deliver rapid, complete, and sustained headache relief without causing side effects that prevent a patient from returning to work or usual activities.

Greater occipital nerve blocks are an emerging migraine treatment modality that are discussed increasingly in the headache and pain literature. Excitement about this procedure is partially fueled by the continuing need for effective treatment. A greater occipital nerve block is a peripheral nerve block that provides regional anesthesia. Using a small gauge needle, a small volume of a topical anesthetic is injected into the subcutaneous tissues at the back of the skull, where the greater occipital nerve lies. Though neither efficacy nor mechanism have been well established for migraine, this procedure is hypothesized to work by decreasing transmission through the trigeminocervical complex (TCC). The TCC is believed to be an important way station in migraine pathogenesis. Within the TNC, nociceptive input arriving from the trigeminal nerve is relayed to second order nerves that terminate in the thalamus. As with the trigeminal nerve, upper cervical nerves, including the greater occipital nerve also terminate in the TCC. It is believed that nerve fibers originating from the upper cervical nerves converge on the same second order nerves as the trigeminal nerve fibers. Decreasing transmission of sensory input through the TCC by blocking the greater occipital nerve can relieve the pain of acute migraine by blocking transmission through the TCC.

Evidence supporting this hypothesis is limited. For the most part, published studies on greater occipital nerve blocks for migraine patients use a non-experimental design and are rife with bias. The goal of this proposed study is to provide sufficient evidence to support or refute a claim of efficacy. We fear that patients who present to an ED with acute migraine may be reluctant to accept treatment with an injection to the scalp as a first-line therapy. Therefore, we will test this hypothesis among patients who have already received first-line treatment in the ED and who require additional medication for refractory pain.

While efficacy data supporting greater occipital nerve blocks is lacking, there is a large amount of data supporting safety. Adverse events include pain at the site of injection, numbness and tingling at site of injection, infection of the injection site, dizziness, and allergic reaction to local anesthetics. The major complication of any peripheral nerve block is intravascular injection into major vessels which can have systemic effects. These effects can be avoided by aspirating prior to injection to ensure no blood return.

Emergency clinicians are adept at performing peripheral nerve blocks. Digital, wrist, foot, penile, and facial nerve blocks are commonly performed in typical emergency care. As the technique for an occipital nerve block is identical, we believe this procedure, if efficacious, will be embraced by the emergency medicine community.

**Hypothesis:** In a population of patients who present to an ED with acute migraine and have been treated with parenteral metoclopramide unsuccessfully, bilateral greater occipital nerve blocks with bupivacaine will provide greater rates of short-term and sustained headache freedom than bupivacaine injected intradermally.

## Methods.

**Study Overview:** This will be a randomized, double-blind clinical trial comparing an active treatment of acute migraine versus placebo in an emergency department after the standard of care for acute migraine has already been administered. The Albert Einstein College of Medicine IRB will provide ethical oversight. The trial will be registered at <http://www.clinicaltrials.gov>.

**Setting:** This study is to be performed in the emergency departments of Montefiore Medical Center. Salaried, trained, bilingual (English and Spanish) technician-level research associates, who execute research studies under the supervision of the principal investigators, staff the emergency department 24 hours per day/ seven days per week and will collect outcome data for this study.

**Selection of Participants:** Eligible patients are adults who present with an acute moderate or severe headache meeting migraine headache criteria, as defined by the International Classification of Headache Disorders-3 $\beta$  (1.1, migraine without aura). Patients who meet criteria for Probable Migraine without Aura (1.5.1) will also be included, provided they have had at least one similar attack previously. Status migrainosus, prolonged duration of headache (>72 hours), or early presentation (<4 hours) do not preclude participation. Patients are to be enrolled if they fail first line parenteral migraine therapy. Specifically, we will require patients to have received metoclopramide for treatment of migraine during the ED visit and to request additional treatment for persistent moderate or severe headache. Patients will be excluded if informed consent cannot be obtained, if there is concern for a secondary cause of headache, if the maximum documented temperature is greater than 100.3 degrees, for a new objective neurologic abnormality, skull defect, suspected infection overlying injection site, known bleeding disorder, ongoing use of anti-platelet agents including P2Y12 platelet inhibitors (clopidogrel, prasugrel, ticagrelor), heparins, warfarin, or 10a inhibitors (rivaroxaban, apixaban, edoxaban, fondaparinux), prior treatment with a greater occipital nerve block, pregnancy, or allergy, intolerance, or contra-indication to the study medication. Patients will be identified by the attending emergency physician and referred to research personnel. Alternatively, research personnel may identify potential participants by searching the ED tracking board, and asking the attending emergency physician if patients are appropriate for the study.

## Intervention:

Active arm) 3cc bupivacaine 0.5% to be injected into the greater occipital nerve region bilaterally  
Sham arm) 0.5cc bupivacaine 0.5% to be injected intradermally in the posterior scalp bilaterally

Formal training sessions will be conducted for those who will inject for research purposes.

Step-by-step procedure for performing bilateral occipital nerve block or sham injection

1. Eligible patient identified.
2. Consent obtained.
3. Research associate hands provider assignment envelope, bottle of 0.5% bupivacaine, 10cc syringe, 27 gauge needle, 2 alcohol swabs and then goes away
4. Provider opens envelope, reads assignment, destroys paper containing assignment
5. Provider draws 3cc bupivacaine into syringe
- 6a. If patient is randomized to active intervention, provider performs GONB: 1) identify occipital protuberance and mastoid process 2) insert 3 cc bupivacaine 1/3 of distance lateral to occipital protuberance, within groove, using fan technique. Repeat procedure on opposite side.

6b. If patient is randomized to sham intervention, provider performs intradermal injection: 1) identify occipital protuberance and mastoid process 2) insert 0.5 ccc bupivacaine intradermally 1/3 of distance lateral to occipital protuberance

7. Provider discards all supplies and summons research associate.

Randomization and Blinding: Study participants and outcome assessors will be blinded. Because the technique will vary depending on assignment, the clinician performing the procedure will not be blinded. A randomization list will be generated using an online generator at <http://www.randomization.com>. Participants will be assigned to active or sham arm in a 1:1 ratio. Assignment will be stratified on baseline pain intensity. Assignment will be placed in an opaque, sealed envelope with sequential study IDs written on the outside. Research personnel will hand the next sequential envelope to the clinician, who will read the assignment and then shred the envelope and its contents. We will give active agent to both study groups to ensure subject blinding. We hope subjects are more likely to believe they got active agent if part of their scalp is numb.

Methods of Measurement: As a primary measure of headache intensity, this study will utilize a standard ordinal headache intensity scale, in which subjects describe their headache as “severe”, “moderate”, “mild”, or “none”. We will also assess pain using an 11-point numerical rating scale (NRS). This latter scale asks subjects to assign their pain a number between 0 and 10, with 0 representing no pain and ten representing the worst pain imaginable. Both of these measures are recommended for use in migraine research by the International Headache Society. We will ascertain overall subject satisfaction with the experimental treatment by asking them if they want to receive the same treatment the next time they come to the ER with a migraine headache. Adverse events will be elicited using a dichotomous question (Did you have any side effects that were caused by the procedure?) followed by an open ended question (Please tell us about the side effects you experienced). Light touch will be assessed in the C2 dermatome. If done correctly, patients will be numb in GON distribution and hopefully migraine free. The number of previous GONB performed will be recorded.

Outcomes: The primary outcome will be the frequency of headache freedom (headache level = none) thirty minutes after completion of the procedure. Important secondary outcomes will be the frequency of sustained headache relief (achieving a pain level of mild or none within one hour of the procedure and maintaining a level of mild or none without the use of additional medication for 48 hours) and subject satisfaction, as evidenced by an affirmative response to the question, do you want to receive the same procedure the next time you come to the ER with migraine. We will also report the improvement in 0 – 10 pain scale between baseline and one hour and the frequency of adverse events.

Protocol: After obtaining informed consent, a brief pain assessment will be performed. A clinician will then inject bilateral GONs (Appendix 1). Research associates will ascertain the patient’s headache level 15, 30, 60, and 120 minutes post-injection. We will ask about the frequency of adverse events 30 minutes after the injection. We will also perform an assessment of light touch and allodynia before and after the procedure (Appendix 2 and Figure). Research associates will contact subjects by telephone 48 hours after ED discharge to ascertain headache status, satisfaction with treatment, and presence of adverse events.

Sample Size calculation: We chose a frequency of headache freedom of 50% as the lowest frequency of success for which clinicians would be willing to perform this procedure. We hope to minimize the placebo effect on the primary outcome by requiring headache freedom rather than just headache improvement. It is unlikely that a patient would progress from moderate/ severe headache to headache freedom within 30 minutes without intervention. We estimated a placebo rate of headache freedom of 20%. Using an alpha of 0.05 and a beta of

0.20, we calculated the need for 39 subjects in each arm. The study will continue until 78 patients have provided primary outcome data.

Analysis: The primary outcome is the rate of headache freedom at 30 minutes. Absolute risk reduction and number needed to treat will be reported with 95%CI. All dichotomous secondary outcomes will be reported as frequencies with 95%CI. Improvement in numerical rating scale will be reported as mean with 95%CI. The primary goal of this analysis is to demonstrate efficacy. If we do not demonstrate statistically significant differences but do see a signal through the noise, we will use the point estimates to decide the feasibility of another study. We will determine the between-group difference (absolute risk reduction) in rates of headache freedom and report this with 95%CI.

Data safety and monitoring: The goal of the data safety committee will be to review study protocol and adverse events on an ongoing basis to determine if risk to subjects can be minimized further without compromising study integrity. Because the overall sample size is relatively small and it will be important to report our findings with sufficient precision, the study will not be halted early for efficacy or futility.

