### Appendix 1. Step-by-step procedure for performing bilateral occipital nerve block or sham injection

1. Research associate identifies eligible patient.
2. Research associate obtains consent
3. Research associate hands provider assignment envelope (lowest available study ID), bottle of 0.5% bupivacaine, 10cc syringe, 27 gauge needle, 2 alcohol swabs. Research associate then returns to research desk.
4. Provider opens envelope, reads assignment, destroys paper containing assignment
5. Provider draws 6cc bupivacaine into syringe
- 6a. If patient is randomized to active intervention, provider performs GONB: 1) identify occipital protuberance and mastoid process 2) after negative aspiration insert 3 cc bupivacaine 1/3 of distance lateral to occipital protuberance, within groove, using fan technique. Repeat procedure on opposite side.
- 6b. If patient is randomized to sham intervention, provider performs intradermal injection: 1) identify occipital protuberance and mastoid process 2) insert 0.5 cc bupivacaine intradermally 1/3 of distance lateral to occipital protuberance
7. Provider discards all supplies and summons research associate.

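### The two injection step lists disagree on volume drawn and on aspiration, and neither tells the clinician to give the sham on the second side

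*Combined protocol and SAP*

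**What the plan says.** The injection procedure appears as a numbered list under Methods, Intervention, and again in Appendix 1, under the same title.

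- **Volume drawn.** Methods step 5: "Provider draws 3cc bupivacaine into syringe". Appendix 1 step 5: "Provider draws 6cc bupivacaine into syringe".
- **Active injection.** Methods step 6a: "insert 3 cc bupivacaine 1/3 of distance lateral to occipital protuberance, within groove, using fan technique. Repeat procedure on opposite side". Appendix 1 step 6a gives the same volume, site, technique and repeat, but opens with a condition: "after negative aspiration insert 3 cc bupivacaine".
- **Safety rationale.** The Overview names intravascular injection as the major complication of a peripheral nerve block and says of its systemic effects: "These effects can be avoided by aspirating prior to injection to ensure no blood return".
- **Sham injection.** The arm definition under Intervention reads "0.5cc bupivacaine 0.5% to be injected intradermally in the posterior scalp bilaterally". Appendix 1 step 6b reads "insert 0.5 cc bupivacaine intradermally 1/3 of distance lateral to occipital protuberance" and stops there. Methods step 6b is the same apart from a typing error in the unit. Neither step 6b mentions a second side.

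The Protocol paragraph in Methods cites Appendix 1 for the injection. The Intervention section plans formal training for injectors.

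**The concern.** The injection is the exposure under test, so its description should yield one procedure. Here a clinician working from the Methods list has too little drug in the syringe for that list's own next step, and is not told to aspirate. A clinician working from either list is not told to give the sham on the second side.

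Three things are at stake. First, an active block given at less than the instructed volume, or on one side, would dilute the contrast with sham. Second, a step on which the protocol's safety case depends is missing from one of the two places where a clinician would look. Third, the Randomization and Blinding paragraph relies on scalp numbness to keep patients blind. Under Appendix 2, research associates test light touch on both sides, including over the injection site, 15 minutes after the procedure, and research associates also collect the 30-minute headache rating. Numbness on one side only could hint at allocation to patient and assessor before a self-reported primary outcome.

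A deviation might also leave no trace. Neither list includes a step that records volume or sides delivered. The research associate leaves at step 3, the assignment paper is destroyed at step 4, and supplies are discarded at step 7.

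**Working it through.** **Active arm: volume needed against volume drawn**

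Inputs: 3 cc per side and a repeat on the other side (step 6a, both lists); 3 cc drawn (Methods step 5); 6 cc drawn (Appendix 1 step 5).

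Volume needed = volume per side × sides = 3 × 2 = 6 cc.

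| List | Drawn | Needed | Shortfall | Per side if one draw is split |
|---|---|---|---|---|
| Methods | 3 cc | 6 cc | 3 cc (50%) | 1.5 cc |
| Appendix 1 | 6 cc | 6 cc | 0 | 3 cc |

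At 0.5% (5 mg per cc), the syringe holds 15 mg in one list and 30 mg in the other. These are amounts drawn. The amount instructed for injection is 30 mg in both.

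**Sham arm**

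- Arm definition, read as 0.5 cc on each of two sides: 0.5 × 2 = 1.0 cc.
- Step 6b read literally, in either list: 0.5 × 1 = 0.5 cc.

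Either draw covers the sham, so this gap concerns sides and not supply. It lies between step 6b and the arm definition, not between the two lists.

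**Aspiration**

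The Overview relies on it, Appendix 1 step 6a requires it, and Methods step 6a is silent. No text says not to aspirate, so this is an omission rather than an opposite instruction. Neither step 6b mentions aspiration.

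**Sample size and sensitivity to incomplete delivery**

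The plan's one computed figure is 39 per arm, for 50% against 20% with alpha 0.05 and beta 0.20. With a two-sided test and no continuity correction:

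n = [1.96 × √(2 × 0.35 × 0.65) + 0.842 × √(0.50 × 0.50 + 0.20 × 0.80)]² / 0.30² = 38.5, rounded up to 39.

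This reproduces the plan, with power of 80.5% at 39 per arm. The inconsistency does not change the calculation, but there is little slack. The documents give no rate of incomplete delivery. As an assumption only, suppose 10% to 20% of active patients responded at the sham rate:

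- 10%: active rate = 0.9 × 50% + 0.1 × 20% = 47%, power about 72%.
- 20%: active rate = 0.8 × 50% + 0.2 × 20% = 44%, power about 63%.

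This shows sensitivity and is not a forecast.

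**The case against.** The best defence is that the intended procedure can be recovered from the text. Both versions of step 6a instruct the same active volume per side, with "Repeat procedure on opposite side" following. Step 3 supplies a bottle and a 10 cc syringe, and supplies are discarded only at step 7, so the syringe can be refilled. The Protocol paragraph points to Appendix 1, where the draw matches the need and aspiration is present. Injectors will be trained. For the sham, the arm definition says both sides, both list titles contain the word bilateral, and the Appendix 2 sensory check presupposes injection sites on both sides.

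Most of this stands, and it rules out two stronger readings that a reader might infer. One is that the active dose differs two-fold according to the page followed. The documents do not support that: the two-fold difference is in what is drawn, not in what is to be injected. The other is that the lists contradict each other on whether the sham is two-sided. They do not: their step 6b is the same, so sham delivery cannot depend on which list is used.

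The defence does not remove the problem. No step calls for a second draw. Nothing says that Appendix 1 overrides the Methods list, and the documents do not say which list will be taught. Following Appendix 1 does not mend step 6b. In the list titles, bilateral can be read as describing the nerve block alone.

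**Conclusion.** The procedure is wrong as written in three respects:

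1. Step 5 differs between the lists (3 cc against 6 cc), and the Methods draw is half of what its own step 6a requires.
2. Aspiration is missing from the Methods list although the protocol's safety case rests on it.
3. Step 6b in both lists omits the second side that the arm definition requires (0.5 cc against 1.0 cc).

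This is more than clerical, because it concerns the tested exposure and a safety step. It alters no endpoint, analysis or sample size.

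It would be tempting to conclude that what patients receive will depend on which page the clinician follows. The documents support only that incomplete active delivery, or a one-sided sham, could occur. How often is unknown, and the harm to blinding depends on a one-sided sham actually being given.

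**What to change.** Reconcile the Methods list with Appendix 1, and both with the Overview on aspiration, into a single step list; the other section should only refer to it. For each arm, that list should state:

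- the volume drawn;
- the volume per side and in total;
- whether aspiration is done;
- whether the procedure is repeated on the opposite side.

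The arms differ by design, so the entries need not match between arms; what must match is every place where the procedure is described. Which instruction is clinically right is for the investigator to settle, and no position is taken here. The cost is protocol wording and one slide in the injector training already planned.

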### Appendix 2. Assessment of light touch and allodynia

Prior to procedure and 15 minutes after the procedure, research associates will assess light touch sensation and allodynia in 6 locations around the scalp: bilateral forehead, bilateral upper posterior scalp, and bilateral lower posterior scalp overlying the injection site (see figure). Using a piece of gauze, research associates will gently stroke each area 4 times and ask two questions: 1) Did you feel that? 2) Did that hurt?

[figure not shown]

Figure: Locations at which allodynia and light touch will be assessed before and after intervention

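### With no symptom check before the injection, each arm's adverse-event frequency can include symptoms that were already present; the comparison between arms is only slightly affected

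*Combined protocol and SAP*

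**What the plan says.** All places are in the combined protocol and SAP.

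- **Prior drug.** Selection of Participants: "we will require patients to have received metoclopramide for treatment of migraine during the ED visit". No interval between that drug and the injection is given.
- **Background symptoms.** The Overview describes common acute migraine drugs as "burdened by a host of nuisance side effects including drowsiness, dizziness, and restlessness".
- **Expected effects of the block.** The Overview lists injection-site pain and "numbness and tingling at site of injection, infection of the injection site, dizziness, and allergic reaction to local anesthetics".
- **Before the injection.** The Protocol paragraph: "After obtaining informed consent, a brief pain assessment will be performed". Appendix 2: "Prior to procedure and 15 minutes after the procedure, research associates will assess light touch sensation and allodynia in 6 locations around the scalp". No other symptom is recorded.
- **After the injection.** The Protocol paragraph: "We will ask about the frequency of adverse events 30 minutes after the injection", then a telephone call 48 hours after discharge "to ascertain headache status, satisfaction with treatment, and presence of adverse events". The Data Safety and Monitoring Section instead has half-hourly enquiry in the ED plus the 48-hour call, and names no time before the injection.
- **The question.** Methods of Measurement asks whether the patient had side effects due to the procedure. The Data Safety and Monitoring Section asks about side effects of the medication, without saying which. Both are followed by an open-ended question.
- **Use.** Outcomes says adverse-event frequency will be reported. Analysis gives dichotomous secondary outcomes as frequencies with 95% confidence intervals; the between-group difference is specified only for headache freedom.

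**The concern.** At least one symptom, dizziness, has two possible sources within one ED visit on the protocol's own account. The plan takes pain and scalp sensation before and after the injection, but side effects only after. A patient who was dizzy or restless before the needle went in, and says so at 30 minutes, cannot be told apart from one whose symptom began afterwards. No rule separates new from pre-existing symptoms. The investigator's causality review is described for serious adverse events only.

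At stake is how the adverse-event percentage in each arm can be read. The Overview gives freedom from activity-limiting side effects as part of the case for a new treatment, so readers are likely to look at the absolute rate after the block.

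**Working it through.** **Plan's own figure.** The plan states no adverse-event rate, so there is none to reproduce on this point. The one plan figure used below is 39 per arm. It reproduces for 50% against 20%, two-sided alpha 0.05 (the plan does not state sidedness) and 80% power, pooled variance, no continuity correction:

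n = [1.96·√(2·0.35·0.65) + 0.8416·√(0.50·0.50 + 0.20·0.80)]² / 0.30² = (1.3221 + 0.5389)² / 0.09 = 38.5, rounded up to 39.

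**Inputs assumed, because the documents give none.**
- e: true rate of adverse events from the procedure, 5% (sham) and 15% (active).
- q: share of patients with such a symptom before the injection, 10% to 30%.
- m: share of those who later report it as a side effect, 10% to 50%. The lower end allows for the question that asks about the procedure.
- Background reporting is the same in both arms and independent of true procedure effects.

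**Formulas.** Reported rate = 1 − (1 − e)(1 − qm). Reported difference = true difference × (1 − qm).

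| q | m | qm | 5% reads as | 15% reads as | Difference (points; true 10) | Ratio (true 3.0) |
|---|---|---|---|---|---|---|
| 10% | 10% | 0.01 | 5.95% | 15.85% | 9.9 | 2.66 |
| 30% | 10% | 0.03 | 7.85% | 17.55% | 9.7 | 2.24 |
| 10% | 50% | 0.05 | 9.75% | 19.25% | 9.5 | 1.97 |
| 20% | 50% | 0.10 | 14.5% | 23.5% | 9.0 | 1.62 |
| 30% | 50% | 0.15 | 19.25% | 27.75% | 8.5 | 1.44 |

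Example, last row: 1 − 0.95 × 0.85 = 0.1925; 1 − 0.85 × 0.85 = 0.2775; 0.10 × 0.85 = 0.085.

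The expected number of patients per arm reporting a pre-existing symptom as a side effect is 39 × qm, from 39 × 0.01 = 0.4 to 39 × 0.15 = 5.9.

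**Dilution against sampling error.** For 5% against 15% with 39 per arm, the 95% half-width of the difference is 1.96·√[(0.0475 + 0.1275)/39] = 0.131, about 13 points. Dilution of 0.1 to 1.5 points is small beside that.

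**Chance imbalance.** The 95% half-width for an imbalance in the background itself is 1.96·√[2q(1 − q)/39], which is 13 points at q = 10% and 20 points at q = 30%. Only the misattributed share of such an imbalance would reach the adverse-event count. Without a pre-injection record it could be neither seen nor adjusted for.

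**The case against.** The strongest reply is that the design already has a control for background symptoms. Allocation is 1:1 against sham, and participants and outcome assessors are blinded. Effects of the first-line drug and of the migraine are therefore balanced in expectation, and the sham rate contains the same background. This stands for the comparison between arms. It does not make either arm's own percentage interpretable, and the plan does not say that it will report the between-arm difference for adverse events.

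A second reply is that the Methods of Measurement question asks the patient to attribute the effect to the procedure. That also stands in part: at m = 10%, a true 5% reads as only 5.95% to 7.85%. But a patient treated twice in one visit cannot reliably say which treatment caused the dizziness. The Data Safety and Monitoring wording gives no such protection, because a truthful report of a metoclopramide effect answers it.

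Third, the stated aim is efficacy, the protocol regards safety as well supported already, and adverse-event frequency is not among the outcomes labelled important. That is a fair reason to rank the point low.

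A reader might go further and infer that the adverse-event comparison favours one arm, or that the efficacy result is compromised. The documents support neither: the background is shared, and headache level is measured separately. Nor do they show that the rates will in fact be inflated by any given amount. The Overview attributes the symptoms to migraine drugs in general, not to metoclopramide by name, and the eligibility text says only that the drug was given in the same visit, not shortly before the injection.

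**Conclusion.** The point holds in a limited form. As written, the plan can count pre-existing symptoms in each arm's adverse-event frequency, and they could not be identified afterwards. On the assumed ranges, a true 5% reads as about 6% to 19% and a true 15% as about 16% to 28%, while the absolute difference loses 1% to 15% of its size. These figures rest wholly on the assumed q and m, on equal background in the two arms, and on independence; they illustrate the mechanism and do not predict the result. The primary outcome and the sample size are unaffected. Severity is minor; the reason to act is that the remedy is cheap and the missing information cannot be reliably recovered later.

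**What to change.** 1. At the existing pre-injection pain assessment, add a neutral symptom check: dizziness, drowsiness, restlessness and other, each present or absent, with severity. It must not ask about cause, since a question about effects of the procedure makes no sense before the procedure.
2. Repeat the check in the same form at every later enquiry, so that worsening can be judged and prompted answers are compared with prompted answers.
3. Count a symptom as an adverse event only if it is new or worse than before the injection. Report pre-existing symptoms in a separate row.
4. Use one adverse-event question, reconciling Methods of Measurement with the Data Safety and Monitoring Section, and one schedule, reconciling the Protocol paragraph with that section.
5. Report the between-arm difference in adverse-event frequency with its 95% confidence interval, beside the per-arm frequencies.

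Cost: a few extra questions at each assessment, asked by research associates who already carry out these assessments, with no extra staff and no change to the sample size. Prompting may raise symptom reporting; with participants and assessors blinded, the rise should be similar in both arms.

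### No between-arm contrast or baseline adjustment is pre-specified for the pain-scale (NRS) change, and no contrast is named for the other secondary outcomes

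*Combined protocol and SAP*

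**What the plan says.** The Analysis paragraph under Methods commits to a contrast for headache freedom: an absolute risk reduction and number needed to treat with 95% CIs, and a closing sentence that promises the between-group difference again. For the rest it says "All dichotomous secondary outcomes will be reported as frequencies with 95%CI. Improvement in numerical rating scale will be reported as mean with 95%CI".

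The Outcomes paragraph defines the NRS measure: "We will also report the improvement in 0 – 10 pain scale between baseline and one hour and the frequency of adverse events". A baseline NRS score must therefore be collected. The same paragraph ranks sustained relief and satisfaction as important secondary outcomes.

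The Hypothesis is comparative beyond the primary endpoint: the nerve block "will provide greater rates of short-term and sustained headache freedom" than the intradermal injection. The Randomization and Blinding paragraph stratifies assignment on baseline pain intensity. No analysis in the plan uses that stratum or the baseline score.

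**The concern.** The authors name an absolute risk reduction or a between-group difference when they want a contrast, and they do so only for headache freedom. The natural reading of the other two sentences is a summary within each arm. A reader would then be given two frequencies or two means, each with its own interval, and no planned estimate of the treatment effect.

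Two things are at stake. First, the choice of effect measure, of adjustment, and even of whether to form a contrast is left open until the data are in. Second, the natural between-arm comparison of raw NRS change uses the baseline score inefficiently. It can be less precise than a baseline-adjusted comparison, and it passes any chance baseline difference into the estimate.

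**Working it through.** **1. The plan's own figure.** Inputs from the Sample Size paragraph: 50% active, 20% sham, alpha 0.05, and beta "0.20, we calculated the need for 39 subjects in each arm". The two-sided pooled formula without continuity correction is

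n = [1.960·√(2·0.35·0.65) + 0.842·√(0.2·0.8 + 0.5·0.5)]² / 0.30² = (1.322 + 0.539)² / 0.09 = 38.5, rounded up to 39.

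This reproduces the stated size (power 80.5%). The sample size is not at fault, and it relates to the primary outcome only.

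**2. NRS: ANCOVA against raw change.** Let s0 and s1 be the baseline and one-hour SDs, r their correlation and k = s0/s1. Per-patient variances:

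- change score: s1²·(1 + k² − 2rk)
- ANCOVA: s1²·(1 − r²)
- proportion saved: (k − r)² / (1 + k² − 2rk)

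The documents give neither r nor k. I assume r from 0.3 to 0.7 and k from 0.5 to 1. A low k is plausible because entry requires persistent moderate or severe pain, which narrows the baseline spread, while one-hour scores can range from 0 to 10.

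| r | saved, k = 1 | saved, k = 0.5 |
|---|---|---|
| 0.3 | 0.49/1.40 = 35% | 0.04/0.95 = 4% |
| 0.5 | 0.25/1.00 = 25% | 0/0.75 = 0% |
| 0.7 | 0.09/0.60 = 15% | 0.04/0.55 = 7% |

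The saving is zero wherever k = r. The range is therefore about 0% to 35%.

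**3. What that means in NRS points.** With 39 per arm and an assumed SD of change of 2.0 to 3.5, the 95% CI half-width for the difference in mean change is 1.96·SD·√(2/39) = 0.89 to 1.55. At the best case of 35%, these become 0.89·√0.65 = 0.72 and 1.55·√0.65 = 1.25. At the worst case they do not change.

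**4. Chance imbalance.** Suppose the arms differ by d at baseline (active minus sham). The within-arm slope of one-hour on baseline score is r/k, so the raw difference in improvement is shifted by (1 − r/k)·d. Over r = 0.3 to 0.7 this runs from 0.7d to 0.3d at k = 1, and from 0.4d to −0.4d at k = 0.5. ANCOVA removes it.

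**5. Dichotomous outcomes.** A contrast needs only per-arm counts. With 20/39 against 10/39 as an invented example, the difference is 51.3% − 25.6% = 25.6 points (from unrounded values). Its standard error is √(0.513·0.487/39 + 0.256·0.744/39) = 0.106, giving a 95% CI of about 4.8 to 46.5 points. Nothing has to be collected to report this.

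**The case against.** The strongest reply is that nothing is lost. The arms are randomized, and anyone can form a risk difference or mean difference from the reported counts, means and intervals. A change score is a valid estimator, and the trial was sized for its primary outcome alone. Most of this stands. It is why the point, for the dichotomous outcomes, is one of pre-specification. It does not cover the NRS in full: a baseline-adjusted estimate cannot be recovered from per-arm mean changes.

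The closing Analysis sentence gives no time point for headache freedom, so it could be read to include the sustained freedom named in the Hypothesis. That is possible, but the listed secondary outcome is sustained relief (mild or none), which the sentence does not cover. Nor does it cover satisfaction, adverse events or the NRS.

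Three stronger readings are tempting and are not supported.

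- A reader might infer that the trial cannot efficiently show a difference on its secondary outcomes. It can; step 5 above shows how.
- A reader might judge each outcome by whether two separate 95% CIs overlap. At 39 per arm and 50% against 20%, that rule has about 52% to 57% power, against 81% for a direct chi-square comparison. But the plan nowhere says overlap will decide anything, and those rates belong to the primary outcome, which does have a planned difference. This is not a loss on any secondary outcome.
- A reader might say regression to the mean biases the change score. Under randomization it acts on both arms alike in expectation, so the contrast is unbiased. Only chance imbalance remains, and the stratification already limits that.

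**Conclusion.** The point holds as a gap in pre-specification and a missed free gain on the NRS. The plan names no between-arm contrast for sustained relief, satisfaction, adverse events or NRS improvement, and no adjustment for baseline pain although it stratifies on it.

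The precision gain from ANCOVA is about 0% to 35% of the variance. It rests on assumed values (r from 0.3 to 0.7, SD ratio from 0.5 to 1), and the upper end requires equal SDs. The restricted entry criterion makes the lower end quite possible. Even there, adjustment protects against chance imbalance within strata whenever r and k differ, at the price of a few degrees of freedom. The primary analysis and the sample size are unaffected.

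**What to change.** Replace the two sentences on secondary outcomes in the Analysis paragraph with text to this effect:

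- The one-hour NRS will be analysed by ANCOVA with arm, baseline NRS and the randomization stratum, and the adjusted between-arm mean difference will be reported with 95% CI.
- For sustained relief, satisfaction and adverse events, the between-arm risk difference will be reported with 95% CI, with the interval method named. Adverse events may be sparse at 39 per arm, so the method should suit small counts.

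Keep the per-arm frequencies and mean improvements as descriptive columns. In the same edit, say whether the sustained endpoint is freedom, as in the Hypothesis, or relief, as in the Outcomes paragraph, so that the contrast attaches to a defined outcome.

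The cost is a few lines of text. The baseline score and the stratum are already part of the design, and no patients, visits or procedures are added.
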